- Quality of life/functional outcome comparisons using the KOOS Jr score, Oxford Knee Score (OKS), numerical rating scales (NRS) of gait/walking ability and sleep.
- Post-operative recovery comparisons using the Quality of Recovery 15 (QoR-15) survey and comparing average length of stay (LoS) for each study group

Questions to be answered:

- Is IORA of Diclofenac or systemic Diclofenac more effective in managing post-operative pain (as judged by VAS-P scores).
- 2. Will IORA of combined Diclofenac or systemic Diclofenac result in a more significant reduction in additional systemic opioid use for post-operative analgesia (as judged by MME).
- 3. Will IORA of Diclofenac or systemic Diclofenac provide better clinical improvement in knee health recovery and outcomes (as judged by KOOS Jr, OKS, NRS gait/walking ability and sleep, QoR-15, LoS).

Study Design

A prospective, double blinded RCT, with a single site cohort.

Patients and Methods

Patients who will be undergoing primary TKA for osteoarthritis will be eligible for this prospective study and randomised into two groups with 23 participants in each, one group receiving IORA Diclofenac (intervention group), and one group receiving IV Diclofenac (control group).

Power Calculation

There is a paucity of data evaluating the efficacy of IORA in pain management following TKA because it is a novel technique, although postoperative pain management is a thoroughly investigated area. Sample size was calculated based on previously published data investigating the efficacy of perioperative Celecoxib (a NSAID) on postoperative pain (VAS pain) after TKA [32]. This study showed statistically significant improvements in VAS pain scores for the intervention group (Celecoxib and PCA Morphine) at 48 hours and 72 hours after TKA, compared to the control group (PCA Morphine only). Mean VAS pain scores (in mm) in the intervention group were 21.3 ± 16.8 at 48 hours, and 17.8 ± 16.6 at 72 hours. Whereas VAS pain scores in the control group were 34.3 ± 15.0 at 48 hours, and 31.7 ± 20.1 at 72 hours.

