This will be achieved via a complete randomisation process using computerised sequence generation (random number generator) in a 1:1 ratio. Sealed, opaque envelopes which have been sequentially numbered will be used as the method of concealment. The envelopes will contain a randomised group allocation and instructions of medication preparation for administration. These will be prepared by an independent member of staff. The envelopes are to be sequentially numbered, as per the generated sequence, in advance for allocation to patients once they have consented to the trial. Once a patient has met the criteria for enrolment and has given informed consent, they will be allocated a randomisation envelope by the investigator or designee. Envelopes will be opened sequentially only after the participant's name has been written on the appropriate envelope. The investigator or designee will note the randomisation number in the patient's Case Report Form and this will be used as the patient's study ID number. Patient's will be blinded to their group allocation.

A patient information leaflet will be provided to the patient at their preoperative clinic appointment. Randomisation is to occur at the time of consent (which is usually the day prior to surgery) to allow for the appropriate orders to be made to ensure the study medication can be administered on time. The assigned envelope will be handed to a researcher on the day of the procedure, who will begin preparing the study medication for the appropriate study group.

Blinding

Patients, surgeons, and anaesthetists will be blinded to group allocation. Patients will be under general anaesthetic at the time of study medication administration, so will not be aware of which mode of study medication has been given. An unblinded researcher will prepare a 10 ml syringe with either normal saline 0.9% (control group), or 75mg Diclofenac made up to 10 mL with normal saline 0.9% (intervention group). The fluid will be passed onto the sterile field for administration by the treating surgeon.

An infusion of either 75mg Diclofenac made up to 100 mL with normal saline 0.9% (intervention group), or 100 mL normal saline 0.9% (control group) will be prepared by an unblinded researcher and handed over to the anaesthetist (blinded) for the preoperativeIV infusion.

Evaluations/Patient Outcome Measurements

Patient Demographics

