Means, standard deviation, and 95% confidence intervals will be calculated for the participant VAS-P scores at each recorded time interval as the primary objective of the study. A general linear model or generalised linear mixed model, followed by independent two-sample t-test or Wilcoxon non-parametric rank sum test will be used to analyse the data. VAS-P scores will be pooled according to the appropriate study group for comparison between the study arms. An MCID of 20 mm will be used to determine a clinically significant difference in pain management (but not necessarily statistical significance).

For secondary objectives, independent two-sample t-test or Wilcoxon non-parametric rank sum test will be used to compare means of MME, LoS, QoR-15, satisfaction, gait, sleep, OKS, KOOS Jr scores between the intervention group and control group.

The intended statistical test used will be dependent on the distribution of the data collected. This will be determined by appropriate normality and homogeneity testing of the data. If requirements

are not met, a transformation may be applied, which will likely be logarithmic. Adjustments will be made accordingly based on the data obtained.

Baseline characteristics and preoperative survey scores will be compared using a two sample t-test or Wilcoxon non-parametric rank sum test. Gender comparisons between the two study groups will need to be analysed using a two-way analysis of variance (ANOVA) or in the case of non-parametric testing, Kruskal-Wallis test.

Adverse events will be recorded separately and reviewed by investigators for relevance to the procedure/intervention as well as commonalities. Frequency and percent distributions will be presented in tabular form and logistic regression will be used for comparison of the study groups.

The statistical principles of this protocol have been reviewed by a Consultant Statistician who will also oversee statistical analysis.

Selection Criteria for Investigators/Sites

- The investigator(s) participating in this study is(are) qualified Orthopaedic surgeon(s).
- Research assistants and study staff will be under the direction of the Principal investigator.
- Conflicts of interest (including financial assistance from other parties) will be declared by Investigators and research personnel before starting the trial.
- A list entailing any persons, their qualifications, and their roles relating to the trial, must be kept by the investigators.

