Appendix 1: Safety of the Intraosseous Route

The use of the intraosseous route for administration of both fluids and medications is well established. In 1947, Heinld [22] reported on the use of the intraosseous route in over 1000 paediatric patients, reporting a 95% success rate in administering fluids, blood products, and a variety of medications. The technique has been more popular in paediatric patients because intravenous access is more difficult; however intraosseous administration is equally as effective in adult patients.

The technique of intraosseous regional administration of antibiotics has been evaluated in humans in multiple randomised controlled trials [9, 10, 11]. No complications related to the use of the technique were found in these studies. Recent retrospective reviews involving large numbers of patients have shown that the IO route comes with minimal risk. Harper et al [23] reported no complications directly related to the IO insertion device out of 119 patients reviewed. Results from a study involving 488 patients in the IO group showed no cases of complications related to IO infusion [24].

The use of regional (with tourniquet inflated) intraosseous infusions of medications has also been investigated in humans. Waisman [7] investigated 109 patients who were given local anaesthetic agents through the regional intraosseous route, in both the upper and lower limbs, to allow surgical procedures to be performed on the limb with the patient awake. The procedure was successful in 106 of 109 patients, with 3 failures. In one patient the needle was incorrectly positioned, and two patients had inadequate anaesthesia which the authors attributed to an insufficient amount of medication infused. No other complications were reported. This paper is a useful reference as it has a very similar concept to our study (substituting the intraosseous route for intravenous in the regional delivery of medications) and provides evidence of the safety of the technique in a large number of patients.

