IO access has potential risks. The inability to inject at the site indicates incorrect placement of the needle (not in the medullary space). Extravasation into soft tissues is the most common complication, commonly caused by cortical disruption from multiple attempts into the same site, dislodging of the needle into the soft tissues or misplacement. This may lead to other complications such as compartment syndrome, cellulitis, osteomyelitis, fat embolism, inability to remove IO needle. These complications are rare, with an overall incidence of <1% [4].

There are 4 main complications of intraosseous infusion that have been reported in adults. All relate to technical errors or prolonged infusions in an emergent setting, and are therefore extremely unlikely to occur in the single, controlled injection proposed in this study.

1) Extravasation of fluid (due to incorrect needle placement)

This complication occurs when a needle is not placed correctly (outside the bone), and infusion of fluid or medication is commenced. With modern intraosseous needles this complication is reduced by closely monitoring the patient, particularly at the IO needle insertion site, and using appropriate length IO needles to prevent over penetration through the bone. The reported success rates for the EZ-IO needle used in the current study range from 94-100%, and it is anticipated that as the needle will be placed by a trained orthopaedic surgeon in a controlled theatre environment the chance of incorrect needle placement will be very low.

2) Compartment Syndrome

Compartment syndrome again relates firstly to incorrect needle placement and has been described rarely in an isolated case report following intraosseous infusions [27]. It occurs if the tip of the needle is placed into soft tissues rather than bone, then prolonged infusion of fluids is commenced without recognition of the situation, leading to increased pressures within tissues. Llarge published series of intraosseous infusions have not reported this complication suggesting it is very rare [26]. It is extremely unlikely to occur in the context of this study as the needle is left in situ for a very short time, and fluid is injected as a single bolus so needle malposition or fluid leakage into the tissue will be immediately recognised.

3) Fracture

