There have been isolated reports of fracture following intraosseous needle placement in the literature. This is thought to relate to the use of excessive force with manual needle placement, and to our knowledge has not been reported with the powered needle driver used in the current study.

4) Infection / osteomyelitis

A meta-analysis of 4359 intraosseous insertion attempts reported an incidence of infection of 0.6% [26]. It is anticipated that as the insertions in our study will take place in a fully sterile environment and antibiotic will be injected through the needle the incidence of infection is likely to be even lower.

The above complications will be outlined in the patient information sheet.

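### Logistic regression is the only adverse event comparison named; at 23 per arm an uncommon event often leaves exactly one arm empty, and the ordinary fit then has no finite odds ratio or usable Wald p-value

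*Protocol*

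**What the plan says.** The adverse event sentence in Data Capture and Analysis plans tables of counts and percentages and adds that "logistic regression will be used for comparison of the study groups". No exact, penalised or purely descriptive alternative is given. The same section lets the choice of test depend on the distribution of the data. That choice rests on normality and homogeneity checks and a probable log transformation, which do not apply to a yes/no outcome.

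Patients are "randomised into two groups with 23 participants in each", by "computerised sequence generation (random number generator) in a 1:1 ratio".

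Appendix 1 gives the only event rates. Of the complications of intraosseous access it says "These complications are rare, with an overall incidence of <1% [4". It cites a meta-analysis with 0.6% infection, and one series in which "Results from a study involving 488 patients in the IO group showed no cases of complications related to IO infusion". The Protocol gives no expected rate for any other adverse event. Its definition (Definitions and Reporting of Adverse Events) takes in any undesirable clinical occurrence, so common events count too.

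**The concern.** Logistic regression by maximum likelihood needs at least one event and one non-event in each arm to give a finite odds ratio. If one arm has no events, the likelihood keeps rising as the log odds ratio moves away from zero. The software stops wherever its tolerance or iteration limit tells it to, and the standard error grows faster than the coefficient. The usual output is then a huge odds ratio, a meaningless interval and a Wald p-value near 1, however large the imbalance.

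Twenty-three per arm is small enough for this to happen often with uncommon events. Part of the stated rationale for the regional route is fewer systemic adverse effects, so the comparison between arms has some bearing on what the trial may claim.

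**Working it through.** The Protocol states no figure for the adverse event comparison, so there is none to reproduce. Its sample size rests on pain scores alone.

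**Inputs.** n = 23 per arm, 1:1 (Patients and Methods; Randomisation). Event rate p, equal in both arms: 0.6% and 1% reflect Appendix 1 (1% is the upper end of its below-1% figure); 2% to 20% are assumptions.

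**How often an arm is empty.** Let q = (1 − p)^23 be the chance that one arm has no event.
- Neither arm has an event: q²
- Exactly one arm is empty: 2q(1 − q)
- Exactly one empty, given at least one event: 2q(1 − q) / (1 − q²)

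At p = 1%: q = 0.99^23 = 0.794. Then q² = 0.630, 2 × 0.794 × 0.206 = 0.328, and 0.328 / 0.370 = 0.885.

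| Rate p | q | No events at all | Exactly one arm empty | One empty, given any event |
|---|---|---|---|---|
| 0.6% | 0.871 | 75.8% | 22.5% | 93.1% |
| 1% | 0.794 | 63.0% | 32.8% | 88.5% |
| 2% | 0.628 | 39.5% | 46.7% | 77.2% |
| 5% | 0.307 | 9.4% | 42.6% | 47.0% |
| 10% | 0.089 | 0.8% | 16.2% | 16.3% |
| 20% | 0.006 | 0.0% | 1.2% | 1.2% |

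The column that counts against logistic regression is the fourth. With no event in either arm (third column), Fisher's test cannot compare the arms either.

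**What the fit returns with one empty arm.** Take 6/23 versus 0/23.
- Fisher's exact test: p = 2 × C(23,6) / C(46,6) = 2 × 100,947 / 9,366,819 = 0.022.
- Newton fitting from zero: each step moves the log odds ratio about one unit further out. The Wald p-value is 0.69 after 8 steps, 0.86 after 10, 0.98 after 15 and 0.998 after 20. A standard generalised linear model routine stops at a log odds ratio of about −22.5 with standard error about 16,569, giving p = 0.999.
- The Wald p-value therefore depends on the stopping rule. At 7/23 versus 0/23 the same routine gives 0.999 against Fisher's 0.009.

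**Likelihood-ratio test from the same model.** It gives 0.0024 for 6 versus 0, so it does not miss that imbalance. It errs in the other direction. For 3 versus 0 it gives 0.037, yet with three events in all a 3–0 split either way arises by chance with probability 2 × C(23,3) / C(46,3) = 2 × 1,771 / 15,180 = 0.233. By enumeration, its true size at a nominal 5% is 6.5% at a 5% event rate and 8.3% at 10%. At rates of 1% and 2% the overall size is 0.2% and 1.3%, because most tables then hold too few events to reject.

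**What can be said from an empty arm.** The exact two-sided 95% upper limit for 0/23 is 1 − 0.025^(1/23) = 14.8%.

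**The case against.** Several points on the other side stand.

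- A reader might add the two kinds of empty table and infer that the method fails 96% of the time at a 1% rate (63.0% + 32.8%, before rounding). The larger part has no events at all, where no method helps, so 33% is the figure that applies.
- A reader might infer that the safety comparison fails for most event types. The Protocol does not support that. Its adverse event definition covers common events; at 20% a zero arm arises in about 1% of tables. Nor does it say that a separate model is fitted to every rare event.
- A reader might infer that a safety signal would be hidden. Counts and percentages are tabulated and adverse events are reviewed, so 6 versus 0 would be seen. Such a split also does not belong to the quoted rates: at 1%, six or more events among 23 has probability about 9 × 10⁻⁸. Fisher's test needs at least 5 versus 0 (p = 0.049), and five or more in an arm has probability about 3 × 10⁻⁶. At those rates it would almost never signal either.
- The quoted rates concern intraosseous access. Both arms receive an intraosseous injection and intraosseous vancomycin, so that risk is largely shared.
- It would be too absolute to say that logistic regression yields no p-value. The Protocol does not specify Wald inference, likelihood-ratio and score tests can be computed, and Firth-penalised and exact versions are forms of logistic regression. An analysis plan not shown here could name one.

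These points narrow the concern without removing it. The Protocol itself names the method, without qualification, and its stated flexibility does not reach binary data. The ordinary fit is what most readers would run, and it breaks down when exactly one arm is empty.

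**Conclusion.** The concern holds in a limited form. For uncommon events, roughly 1% to 5%, the only between-group method named will meet a table with exactly one empty arm in about a third to a half of cases (33% to 47%). There the ordinary maximum-likelihood odds ratio is infinite and the Wald p-value arbitrary.

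This assumes equal rates in both arms, 23 evaluable patients in each, and event rates that, beyond the two Appendix 1 figures, are assumed. At 10% the problem arises in 16% of tables and at 20% in about 1%.

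Severity is minor: the descriptive tables are planned regardless, this is a safety summary, and the primary outcome is untouched.

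**What to change.** Replace the logistic regression clause in Data Capture and Analysis with wording such as: adverse events will be presented as the number and percentage of patients by arm, with the risk difference and an exact 95% confidence interval; where a between-group comparison is wanted, Fisher's exact test will be used; if covariate adjustment is needed, Firth-penalised or exact logistic regression will be used.

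The cost is one sentence and no new data; because the Protocol bars changes without written Ethics Committee approval, it needs that approval. It is best settled before allocation is revealed, so that the method is not chosen with the counts in view.

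The downside is that Fisher's test is somewhat conservative: its true size here is 0.3% at a 5% event rate, 1.6% at 10% and 2.5% at 20%. The risk difference and its interval should therefore carry the interpretation rather than the p-value.

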- NRS for gait/walking ability, sleep. To be recorded for 1 week post-op.
- Participant length of hospital stay, from date of admission to date of discharge.
- NRS for patient satisfaction, recorded at post-op weeks 2 and 6.
- KOOS, JR scores at post-op weeks 2 and 6.
- OKS at post-op week 6.

Indirect measure of pain will be gauged from the total MME dosing for each patient which will be an indicator of postoperative opioid use burden. Patients will be required to record in their pain diaries the amount, in milligrams, of additional opioid medication they are taking per day up to post-op day 7, which will then be converted into daily MME. Patients will also be required to record on a NRS how much pain has interfered with their walking ability and sleep over the previous 24 hours, up to post-op day 7 in their pain diaries.

[figure not shown]
An automated texting service will be used to remind patients to fill out their pain diary.

Length of stay from date of admission to date of discharge will be recorded for all participants on their pain diaries. Average length of stay will be calculated for each study group and compared.

Participants will be followed up in a 2 week post-op clinic where the pain diaries are to be collected. At this clinic, participants will be required to complete a KOOS Jr survey and NRS for patient satisfaction relating to their knee replacement. At the 6-week post-op mark patients will be seen in clinic again and will be required to complete a KOOS Jr survey, patient satisfaction NRS, and OKS. The means of these outcomes will be compared between the study groups at each particular time point.

Participants will be provided patient information leaflets detailing potential adverse effects of Diclofenac. If any adverse effects occur, participants are to report to nursing staff, who will inform the treating doctor/researcher. We predict side effects from a single preoperative dose of Diclofenac are unlikely to arise after discharge i.e., a few days post-op.

Study Timeline

Data Capture and Analysis

Data will be recorded on Case Report Forms (CRFs; includes patient pain diaries). An investigator will complete and sign forms once they are completed by patients. The data will then be entered onto a secure excel spreadsheet by a research assistant. The original paper CRFs are to be stored securely, and archiving to be undertaken in accordance with ICH/GCP guidelines.

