The clinical research team will be responsible for monitoring the trial site to ensure compliance with the study protocol and capture of any data or complications not already documented. Data will also be verified from source documents. A Data Safety Committee has not yet been formed, but will be formed prior to beginning the study. This should comprise of the Principal Investigator, a statistical advisor and a patient advocate will be formed to review the data and any adverse event forms.

IRAD Study Study Study Protocol

Management of Concurrent Events

Concurrent Illness/Procedures

Where participants experience inter-current illnesses or adverse events, any required concurrent procedures or medications will not be restricted during the study. Given the demographics of patients receiving total knee joint replacements, it can reasonably be expected that this may occur.

Withdrawal from Study

All study participants will be advised that they may voluntarily withdraw from the study at any stage, for any reason, and they have no obligation to state their reasoning. This will not affect their medical care. Even so, efforts will be made to try to determine the reason for withdrawal. A letter detailing their desire to withdraw from the study may be requested by an investigator. For all participants lost to follow up, attempts to locate them will be documented.

Circumstances for which a patient would be determined as not continuing in the study:

- Completion/termination of study
- Death
- Concurrent illness
- Lost to follow-up
- Other

Investigators may also choose to withdraw participants if they are unable to continue participation in the study due to some condition unrelated to this study.

For all participants who withdraw from the study, a Study Completion Form will be completed.

Emergency Unblinding

Unbinding of participant treatment allocation may be required in the case of an adverse event. In such cases, if deemed necessary by the principal investigator, the participant's allocation may be revealed by the principal investigator, or a designee.

Modification of Protocol

Unless written approval from the applicable Ethics Committee has been obtained, there will be NO modifications made to this study protocol.

Any deviations to this study protocol will be detailed on a Protocol Deviation Form as soon as identified. Notification to the applicable Ethics Committee will be made according to the Ethics Committee requirements.

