Definitions and Reporting of Adverse Events

Definitions

Adverse Events:

Any undesirable clinical occurrence in a subject, whether it is considered to be study
medication related or not, that includes a clinical sign, symptom, or condition; and/or an
observation of an unintended technical procedural error.

Expected:

An adverse event is expected when the specificity and severity of the event is consistent with
a complication that is not related to the study specific medications or procedural technique,
but may be related to the surgical procedure

Unexpected:

• An adverse event is unexpected when the specificity or severity of an adverse event is not consistent with the standard. It refers to an adverse event that has not been observed before

Adverse Study Medication Event:

• A clinical sign, symptom or condition that is causally related to the product, administration of the product, or performance of the product.

Serious Adverse Event:

- Any untoward medical occurrence that:
 - Results in death,
 - Is life threatening,
 - Requires inpatient hospitalisation or prolongation of hospitalisation,
 - Results in persistent or significant disability/incapacity,
 - May have caused a congenital anomaly/birth defect,
 - Requires intervention to prevent permanent impairment or damage,
 - Is a medically important event or reaction.

IRAD Study Study Study Protocol

Reporting of Events

Adverse Events:

Any adverse event that occurs at any point in time from the beginning of the surgical procedure until either the participant is terminated from the study, or 7 days post-completion, should be recorded as follows:

- All information on general medical, operative, and study medication related complications (adverse events) will be documented on Case Report Forms.
- Information should include date of occurrence, description, severity, relationship to study medication, treatment, and date of resolution.
- The investigator will determine if the event is related to the study medication.
- Any adverse event in a study patient must be monitored until it has resolved or been considered non-clinically significant by the investigator.

Expected Events:

Should be reported to the principal investigator as soon as possible, but not later than five working days after the investigator first learns of the event

Adverse Study Medication Events

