Study staff will ensure that any adverse study medication events which occur will be documented and immediately reported to the principal investigator. They should also be reported to the reviewing Ethics Committee and institution as soon as possible, no later than fifteen working days after the investigator learns of the event. An evaluation of the adverse events will be conducted by the investigator. Following this, if it is determined that the adverse effect presents an unreasonable risk to participants, the trial will be terminated as soon as possible. Termination shall occur no later than five working days after the investigator makes the determination, and no later than fifteen working days after the investigator first receives notice of the adverse event.

Serious Adverse Events (SAEs)

Any adverse event considered to be serious in nature which occurs at any time point from signing of Informed Consent Form until either the patient is terminated from the study, or 7 days post-completion, should be recorded as follows:

- All SAEs should be reported immediately to the principal investigator no later than 24 hours after becoming aware of the event.
- This will be followed promptly by detailed, written reports.

• The investigator should comply with the applicable regulatory requirement(s) related to the reporting of serious unexpected adverse study medication reactions to the regulatory authority (MedSafe NZ) and the Ethics Committee.

 All other SAEs not related to the study medication will be reported to the Ethics Committee as directed.

Ethics Committee

Approval

The investigator is responsible for obtaining Ethics Committee and Governance approval to conduct this study

Prior to Initiation of the Study

Written approval by the Ethics Committee and Governance must be obtained prior to beginning the study. Discussions may be had with prospective participants regarding the study, however written Patient Informed Consent must not be obtained. Until all approvals are granted, study procedures must also not be performed on prospective study participants.

Progress Reports

Progress reports on the trial will be submitted by the investigator at the request of the Ethics Committee.

Final Reports

Upon completion of the investigation, each investigator will submit an Ethics Close-Out Report on his/her part of the investigation within three months of completion of the investigation. This will be submitted to the Ethics Committee.

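### Concurrent illness is listed as a reason for not continuing after a one-dose treatment, and AE/SAE recording ends at termination, so outcomes and new events after an illness-based exit have no stated collection

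*Protocol*

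**What the plan says.** All references are to the Protocol.

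- **Withdrawal from Study** gives a list headed "Circumstances for which a patient would be determined as not continuing in the study". Its entries are completion or termination of the study, death, concurrent illness, loss to follow-up, and other. The illness entry carries no qualifier.
- **The same section** adds a discretionary route: "Investigators may also choose to withdraw participants if they are unable to continue participation in the study". That sentence goes on to require that the condition be unrelated to the study.
- **Concurrent Illness/Procedures**, immediately before, says that where participants have intercurrent illness or adverse events, "any required concurrent procedures or medications will not be restricted during the study". It adds that such events can reasonably be expected in this population.
- **Reporting of Events, Adverse Events** records events from the start of surgery "until either the participant is terminated from the study, or 7 days post-completion". It also requires: "Any adverse event in a study patient must be monitored until it has resolved or been considered non-clinically significant by the investigator".
- **Serious Adverse Events (SAEs)** starts its window at consent and closes it in the same way: "until either the patient is terminated from the study, or 7 days post-completion".
- **Postoperative Outcome Measurements** confirms that treatment is one preoperative dose and predicts that "side effects from a single preoperative dose of Diclofenac are unlikely to arise after discharge". The diary runs to day 7, with clinic assessments at weeks 2 and 6.

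**The concern.** In a trial with continuing treatment, an illness criterion usually governs whether the drug is stopped. Here the drug has already been given in full before skin incision, so after dosing the criterion can act only on observation. A participant who leaves for illness stops contributing pain scores, opioid use and functional outcomes, and the two safety windows close for that person.

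Such a loss is unlikely to be random. It depends on postoperative health, and the protocol's own rationale is that the regional route reduces systemic adverse effects (Rationale for IORA of Analgesics). Appendix 2 names gastrointestinal bleeding and acute kidney injury as NSAID harms. Appendix 1 names infection and compartment syndrome as possible intraosseous harms. On the protocol's own reasoning, illness could therefore differ by arm. The day 1 to 7 VAS-P and MME comparisons, the later outcomes, and the between-arm logistic regression of adverse events in Data Capture and Analysis would all be exposed.

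**Working it through.** **Step 1. The two statements on illness.** Concurrent Illness/Procedures treats illness as something that happens during participation. Withdrawal from Study lists it as a reason participation ends. No criterion says which illness leads to which result, so two investigators could handle the same participant differently and both comply.

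**Step 2. What an exit after dosing stops.**

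| Item | Stated collection after an illness-based exit |
|---|---|
| The illness that led to exit | Yes: it arises inside the AE window and must be monitored to resolution |
| Scores and events recorded before exit | Nothing says they are discarded |
| Diary VAS-P, MME, gait and sleep ratings to day 7 | None stated |
| Week 2 and week 6 KOOS Jr and satisfaction; week 6 OKS | None stated |
| New AEs and SAEs | None: the window closes at termination |

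**Step 3. How much observation is at stake.** Taking completion as the week 6 visit, the full safety window ends at 42 + 7 = 49 days. An exit on day *d* leaves 49 − *d* days without stated capture of new events: 46 days for *d* = 3 and 42 days for *d* = 7. The diary holds 7 × 2 = 14 scores. An exit at the end of day 3 forgoes 4 × 2 = 8 of them.

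**Step 4. Possible bias at a time point after exit.** The document gives no illness rate and no pain level for ill participants, so both are assumed. If *k* of 23 participants in one arm leave, and their pain would have been *e* mm above that of the rest, the observed arm mean is too low by *k* × *e* / 23.

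| *k* | *e* = 20 mm | *e* = 30 mm |
|---|---|---|
| 2 | 40/23 = 1.7 mm | 60/23 = 2.6 mm |
| 3 | 60/23 = 2.6 mm | 90/23 = 3.9 mm |

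Against the 20 mm MCID this is about 9% (1.74/20) to 20% (3.91/20). Equal losses of the same kind in both arms would cancel in the difference. A one-week average would be affected less, because scores before exit remain.

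**Step 5. Power.** First, the plan's own figure. Power Calculation gives 22 per arm for more than 95% power at 20 mm and 5% significance (two-sided assumed), plus one per arm for loss. The root mean square of the two arm SDs in the cited celecoxib trial is:

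- 48 h: √((16.8² + 15.0²)/2) = 15.93 mm
- 72 h: √((16.6² + 20.1²)/2) = 18.43 mm

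With 22 per arm, power is 98.6% (normal approximation) or 98.3% (noncentral t) at the 48 h SD, and 94.9% or 94.0% at the 72 h SD. The stated figure is reproduced at 48 h and very nearly at 72 h. The allowance of one participant is 1/23 = 4.3%. For larger assumed losses, noncentral t gives:

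| Lost per arm | Left per arm | SD 15.93 | SD 18.43 |
|---|---|---|---|
| 2 | 21 | 97.8% | 92.9% |
| 3 | 20 | 97.2% | 91.7% |
| 4 | 19 | 96.5% | 90.2% |

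Power falls by only a few points. The issue is selective loss.

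**The case against.** The strongest reply is that the list is a set of end-of-participation codes for the Study Completion Form. It includes completion and death, which cannot be grounds for removal, so it may not order anyone out. Investigator withdrawal is optional and needs both inability to continue and an unrelated condition. The unrestricted-care sentence governs care and does not promise that every ill participant stays. The list speaks of not continuing and the safety windows of termination, without formally linking the two. Data Quality Assurance promises attempts to obtain incomplete data and capture of undocumented complications. The protocol also expects few diclofenac side effects after discharge.

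Much of this stands as a limit on the point. A reader might infer that ill participants vanish from both the pain and the safety data. The text does not support that: a postoperative illness that prompts exit is recordable and followed to resolution, nothing discards earlier scores, and exit is not automatic. For the same reason, a calculation that deletes such participants entirely would overstate the bias.

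It does not answer the core. Even as a code, the entry presupposes that illness can end participation after dosing, and the inability and unrelatedness limits are not attached to it. The natural reading is that a participant who does not continue has been terminated, and nothing says otherwise. The data-quality statements are general and set no rule for those who have left. The expectation about late side effects concerns diclofenac, not the intraosseous complications in Appendix 1.

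**Conclusion.** The point holds in limited form. The protocol lists illness as a reason for not continuing when, after dosing, only follow-up can be stopped, and it closes both safety windows at termination. Later VAS-P, MME, week 2 and week 6 outcomes and new events then have no stated collection, and the loss can depend on outcome or on allocated route. The two statements on illness need reconciling.

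No bias figure can be derived from the document. The range of 1.7 to 3.9 mm rests on assumed one-arm losses of 2 to 3 participants with pain 20 to 30 mm above the rest, and applies only after exit. The power loss is small under the losses examined. How incomplete data are analysed may be set out in the statistical analysis plan and is not part of this point.

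A reader might also infer that the illness entry and the investigator-withdrawal sentence should simply be deleted. That goes too far. Under Allocation Concealment, randomisation occurs at consent, usually the day before surgery, so illness between randomisation and dosing can be a legitimate reason for not proceeding, and the single-dose argument does not reach it. The correction is worthwhile and inexpensive.

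**What to change.** 1. Reconcile Concurrent Illness/Procedures with Withdrawal from Study. Either limit concurrent illness and investigator withdrawal to the period before dosing, or state that after dosing they do not end follow-up.
2. State that the diary and the week 2 and week 6 assessments continue as far as the participant is able, unless consent to follow-up is withdrawn.
3. In both the AE and the SAE sections, replace termination as the end of recording with 7 days after the planned week 6 visit, unless consent to follow-up is withdrawn or the participant dies or is lost to follow-up.

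The cost is protocol wording, with the ethics approval that any modification needs, and some extra effort to obtain diaries and clinic forms from ill participants. Clinical care and the study dose are unaffected.
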